3.1.3. Follow-up Period

Subjects will be followed-up for a minimum of 4 weeks after the last dose of investigational product at the Week 56 visit. The follow-up visit will include B-cell counts and other safety, efficacy, and quality of life assessments.

If B-cell counts have not recovered by the Week 60 visit, subjects not entering the extension study (OPV117059) will remain in Individualized Follow-up until:

- CD19+ B-cell counts and circulating IgG levels are \geq LLN or baseline levels (if $<$ LLN)
- Other criteria for study withdrawal/exit are met (see Section 4.4.3)
- Two years after the last dose of investigational product (whichever comes first).

The Individualized Follow-up assessments should be scheduled approximately every 12 weeks. Subjects who withdraw from treatment will also enter the Individualized Follow-up Period.

Note: Subjects who are hepatitis B surface antigen (HBsAg) negative, hepatitis B core antibody (anti-HBc) positive, and hepatitis B virus (HBV) DNA negative (or if in Japan and HBsAg negative, anti-HBc (HBcAb) negative, but hepatitis B surface antibody [HBsAb] positive) must continue HBV DNA polymerase chain reaction (PCR) monitoring at a minimum of every 12 weeks for 6 months after the last dose of study treatment.

For subjects who participate in the extension study, OPV116910 (also known as COMB157J2301) Week 60 study assessments will be completed before any study-related assessments are performed for the extension study.

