Urine hCG (women only)		X		X		X		X		X		X		X	X	X	X	X	X	X	X	X	X			
HAHA; hsCRP ^g		X						X						X			X			X	X	X	X	X	X	
IgG, IgM, IgA	X	X						X						X			X			X	X	X	X	X	X	
Pharmacodynamic markers ^g	X	X		X		X		X		X		X		X			X			X	X	X	X	X	X	

Period:	Screen	Core Study Period (60 Weeks)																						Early WD ^b	
		BL	Treatment Period (56 Weeks)																				F-up ^b		
Study Week:	-2 to -12 ^a	Day 0	2	4	6	8	10	12	14	16	18	20	22	24	28	32	36	40	44	48	52	56	60 ^b		
Clinic (C) or Phone (P) Visit:	C	C	C	C	C	C	P	C	P	C	P	C	P	C	C	C	C	C	C	C	C	C	C	C	C
Pharmacokinetic sample ^g		X		X		X		X		X		X		X			X			X		X	X	X	X
Pharmacokinetic substudy ^{g,h,i}		←See Table 6-3 for PK-PD substudy visits and sample collection time points→																							
Pharmacogenetics sample ^{g,h}		X																							
Serum banking for JC virus testing		X																							
Neurological symptom questionnaire	X	X	X	X	X	X	X	X	X	X	X	X	X	X	X	X	X	X	X	X	X	X	X	X	X

Abbreviations: [redacted]; admin=administration; [redacted]; BL=Baseline; BLC=B-lymphocyte chemokine; C=clinic visit; [redacted]; F-up=follow-up visit; HAHA=human anti-human antibody; hCG=human chorionic gonadotropin; hsCRP=high sensitivity C-reactive protein; Ig=immunoglobulin; P=phone visit; PD=pharmacodynamic; PK=pharmacokinetic; PV=pemphigus vulgaris; [redacted]; WD=withdrawal.

- a. Screening may be up to 12 weeks for disease consolidation/control and adjustment/stabilization of prednisone/prednisolone dose. Multiple visits (unscheduled) are permitted.
- b. If subject is not entering the extension study and CD19+ B cell counts and circulating IgG levels are below the lower limit of normal at Week 60 (or early withdrawal visit), the subject will transition into Individualized Follow-up (see Table 6-2). Subjects requiring additional hepatitis B virus testing will also return for follow-up visits for 6 months after the last dose.
- c. Vital signs should be taken before each injection of investigational product, at approximately 4 hours after the first dose, and at approximately 1 hour after subsequent doses.
- d. Adverse events (AEs) will be collected from the start of study treatment through the Core Study Period. Serious AEs assessed as related to study participation will be collected from the time a subject consents to participate in the study up to and including any follow-up contact.

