- e. Premedication: Each dose of study treatment will be preceded by acetaminophen/paracetamol and an antihistamine (see Section 5.1.2).
Postdose observation and medication: After the first dose, subjects should stay at the clinic to be monitored for any injection-related AEs for a minimum of 4 hours, with acetaminophen/paracetamol administered again at 4 hours. After subsequent doses, it is recommended that subjects stay at the clinic for a minimum of 1 hour, with acetaminophen/paracetamol self-administered approximately 4 to 6 hours after dosing if needed.
Note: An additional 20-mg loading dose (total of two 20-mg injections) will be administered at Week 0 and Week 4.
- f. Laboratory assessments include hematology, clinical chemistry, and urinalysis. "H" indicates visits with only hematology.
At Screening and Week 60/early withdrawal only—Hepatitis B, Hepatitis C, pneumococcal antibody assay, and toxoid antibody assay.
- g. Collect sample predose on dosing days.
- h. Informed consent must be obtained before collecting samples for optional testing (ie, pharmacogenetics research and pharmacokinetic-pharmacodynamic substudy analyses).
- i. Only sites preidentified to participate in pharmacokinetic-pharmacodynamic substudy. See Table 6-3 for the schedule of visits for sample collection.

Note: Visits from Week 2 through Week 60 to be scheduled within ±3 days of the specified time point. Visits during Individualized Follow-up to be scheduled within ±7 days.

Table 6-2 Time and Events Table: Individualized Follow-up Period

	As applicable ^a								Early WD
Study Week for Core Study Completers:	72	84	96	108	120	132	144	156	
Study Week for Early Withdrawals:	+12	+24	+36	+48	+60	+72	+84	+96	
Adverse events (including SAEs and AEs of special interest) ^b	X	X	X	X	X	X	X	X	X
Concomitant medications	X	X	X	X	X	X	X	X	X
Document steroid dose	X	X	X	X	X	X	X	X	X
Neurological symptoms questionnaire (PML monitoring)	X	X	X	X	X	X	X	X	X
PV lesion mapping	X	X	X	X	X	X	X	X	X
Pregnancy testing (urine) (women) – test monthly for 12 months after the last dose of ofatumumab SC; subjects may test at home during months without a clinic visit	X	X	X	X					X
Hematology	X	X	X	X	X	X	X	X	X
Clinical chemistry	X	X	X	X	X	X	X	X	X
IgG, IgM, IgA	X	X	X	X	X	X	X	X	X
Human anti-human antibody	X								X
Pharmacodynamic markers (flow cytometry)	X	X	X	X	X	X	X	X	X
HBV DNA – if applicable, test every 12 weeks for 6 months after the last dose of ofatumumab SC	PRN	PRN							PRN

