Abbreviations: ALT=alanine aminotransferase; anti-HBc=hepatitis B core antibody; AST=aspartate aminotransferase; [redacted]; BlyS= B-lymphocyte stimulator; [redacted]; HBV=hepatitis B virus; HPF=high powered field; Ig=immunoglobulin; PCR=polymerase chain reaction; RBC=red blood cell; WBC=white blood cell.

- To maintain study blinding, values will not be reported to investigators during the Treatment or Individualized Follow-up Periods. After the Week 60 visit and all Individualized Follow-up visits, the central laboratory (or designee) will provide the laboratory values and notify the investigator whether or not a subject needs to remain in Follow-up.
- Screening and Week 60/early withdrawal only.
- Note:** Refer to the Time and Events Schedule (Table 6-1) and the [redacted] investigator manual for specific timing of individual laboratory assessments. Laboratory reference ranges are provided in Appendix 13.

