6.3.10.2. Hepatitis B Screening and Monitoring

Exclude subjects who are HBsAg positive, regardless of other hepatitis B serologies. If a subject is HBsAg negative and anti-HBc positive, perform HBV DNA. Exclude subjects who are HBV DNA positive.

** In Japan, if a subject is HBsAg negative, anti-HBc (HBcAb) negative, but HBsAb positive, an HBV DNA test will be performed and the subject will be excluded if results are positive (refer to Appendix 2).**

Subjects who are HBsAg negative, anti-HBc positive, and HBV DNA negative may be included in the study, but must undergo HBV DNA PCR monitoring at a minimum of every 12 weeks during the Treatment Period and for 6 months after the last dose. Consult with a physician experienced in the care and management of subjects with hepatitis B to manage/treat subjects who are anti-HBc positive. Antiviral therapy to be initiated if required.

Table 6-6 Hepatitis B Virus Test Result Scenarios for Subject Eligibility

HBsAg	anti-HBc (HBcAb)	HBsAb	HBV DNA	Subject Eligibility and Monitoring
All subjects:				
+ / -	+ / -	+ / -	positive	Exclude subject if positive at screening; discontinue study treatment if positive during study
positive	+ / -	+ / -	+ / -	Exclude subject if positive at screening
negative	positive	+ / -	negative	May enroll subject with physician consult and HBV DNA monitoring during study
Additional for Japan: negative	negative	positive	negative	May enroll subject with physician consult and HBV DNA monitoring during study

+ / - = either positive or negative test result

Abbreviations: HBcAb=hepatitis B core antibody; HBsAb=hepatitis B surface antibody; HBsAg=hepatitis B surface antigen; HBV=hepatitis B virus.

If a subject becomes HBV DNA positive during the course of the study, notify the medical monitor. Discontinue further treatment with investigational product and continue to follow the subject for safety as part of the Follow-up Period.

Extra visits outside those defined in the protocol may be needed for subjects who require hepatitis monitoring.

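### The schedule tables rule out the on-treatment HBV DNA testing that Section 6.3.10.2 requires for admitted anti-HBc-positive subjects, and the Appendix 3 liver-event HBV DNA test covers no eligible subject

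*Protocol*

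**What the plan says.** **The requirement.** Table 6-6 lets in subjects who are HBsAg negative, anti-HBc positive and HBV DNA negative, under the condition "May enroll subject with physician consult and HBV DNA monitoring during study". Section 6.3.10.2 sets the frequency: they "must undergo HBV DNA PCR monitoring at a minimum of every 12 weeks during the Treatment Period and for 6 months after the last dose". A subject who turns HBV DNA positive must stop investigational product.

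**The schedule.** Table 6-1 has no HBV DNA row. Its footnote f reads "At Screening and Week 60/early withdrawal only—Hepatitis B, Hepatitis C, pneumococcal antibody assay, and toxoid antibody assay". Table 6-5 lists HBV DNA PCR inside the hepatitis B block marked b, and footnote b reads "Screening and Week 60/early withdrawal only". SAP Section 12.6.2 names HBV DNA PCR and gives the same two time points.

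**After the last dose.** Footnote b of Table 6-1 says "Subjects requiring additional hepatitis B virus testing will also return for follow-up visits for 6 months after the last dose", and the HBV DNA row of Table 6-2 says "if applicable, test every 12 weeks for 6 months after the last dose of ofatumumab SC". These agree with Section 6.3.10.2.

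**Japan.** Table 6-6 also admits HBsAb-positive, anti-HBc-negative subjects in Japan under the same monitoring condition, without an interval. Section 3.1.3 gives them one for the period after dosing: they "must continue HBV DNA polymerase chain reaction (PCR) monitoring at a minimum of every 12 weeks for 6 months after the last dose".

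**Liver events.** Appendix 3 restricts quantitative HBV DNA at a liver stopping event to subjects with chronic hepatitis B at entry, identified by positive HBsAg. Exclusion criterion 6 in Section 4.3 and Section 6.3.10.2 both bar such subjects.

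**The concern.** For the same subjects and the same period, the protocol gives two instructions that cannot both be followed. Section 6.3.10.2 demands regular HBV DNA testing during dosing; the two schedule footnotes confine hepatitis B testing to the start and end of the Core Study Period.

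The tables are not mere summaries. Section 3 makes adherence to Table 6-1 mandatory, and Section 6.3.10.1 says laboratory assessments must follow Table 6-1 and the laboratory manual. A site that works from the schedule would draw no HBV DNA sample while an anti-CD20 antibody is being given.

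Patient safety is at stake. HBV reactivation is an adverse event of special interest (Section 6.3.2.3), and HBV DNA positivity is the rule for stopping treatment. The eligibility of these subjects depends on the test that the schedule leaves out. The liver-event rule does not act as a backstop, because it is addressed to a group that cannot be enrolled.

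**Working it through.** No sample size, power or alpha figure is involved. The check compares texts and counts visits.

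**Step 1. Does the limit apply to HBV DNA PCR?** Yes. Table 6-5 lists HBV DNA PCR within the block marked b. The items marked b (hepatitis B, hepatitis C, pneumococcal and toxoid antibodies) are the same four named in Table 6-1 footnote f, so the two footnotes state one rule.

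**Step 2. On-treatment tests per completer.** Inputs: a 56-week Treatment Period and an interval of at most 12 weeks (Section 6.3.10.2), counted from the first dose at Week 0.

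- Required: multiples of 12 up to 56, which are Weeks 12, 24, 36 and 48, so 4 tests. The next point is Week 60, which is already scheduled.
- Shown in Tables 6-1 and 6-5: 0.

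**Step 3. Gap between consecutive tests under the footnotes.** Inputs: Screening 2 to 12 weeks before randomization, next test at Week 60.

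- Shortest: 60 − (−2) = 62 weeks; 62 / 12 = 5.2 times the permitted maximum.
- Longest: 60 − (−12) = 72 weeks; 72 / 12 = 6.0 times the permitted maximum.

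A subject who withdraws early is tested at that visit, so the gap is shorter, but there is still no test while dosing continues.

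**Step 4. Doses inside the gap.** Dosing visits are at Weeks 0, 4, …, 56: 56 / 4 + 1 = 15. All 15 fall between the two tests.

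**Step 5. After the last dose.** Week 60, then Weeks 72 and 84 in Table 6-2: 72 − 60 = 12 and 84 − 72 = 12 weeks. The rule is met, so the conflict is confined to treatment.

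**Step 6. Liver-event HBV DNA.** The Appendix 3 trigger requires HBsAg positivity at entry; eligibility requires HBsAg negativity. The overlap is 0 subjects. HBsAg and core IgM serology are still done at any liver stopping event, but HBV DNA is not required there for the anti-HBc-positive subjects who were admitted.

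**Step 7. Japanese HBsAb-only group.** Table 6-6 requires monitoring, Section 3.1.3 gives an interval only after dosing, and Appendix 2 adds a screening test but no interval. No on-treatment interval is stated, and the same two footnotes apply.

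**Step 8. Feasibility.** Table 6-1 shows Weeks 12, 24, 36 and 48 as clinic visits with full laboratory testing. The liver-event panel in Appendix 13 already contains quantitative HBV DNA PCR.

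**The case against.** The best reply is that the requirement exists, is explicit and sits where sites must look. A site can admit such a subject only by applying Section 6.3.10.2 and Table 6-6, and a specific rule for a subgroup would normally prevail over a general schedule footnote. The section also warns sites that the schedule may not be complete: "Extra visits outside those defined in the protocol may be needed for subjects who require hepatitis monitoring". Section 3.1.3 speaks of continuing the monitoring after the last dose, which presupposes testing on treatment and suggests the same interval for the Japanese group. Table 6-5 also points to a laboratory manual that is not available here and may schedule the test.

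Further, ALT and AST are measured during dosing with stopping rules attached, and a liver stopping event already halts treatment. SAP Section 12.6.2 governs listings rather than sampling, and it separately lists end-of-monitoring information. The programme was terminated, so few subjects may be affected, possibly none.

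Much of this stands. A careful site could get it right. The defect is a contradiction rather than a missing requirement or a poor design choice, and the liver-event and SAP points are secondary. But none of it removes *only* from two footnotes in tables that bind the sites. The allowance for extra visits creates no exception to them. Liver enzymes do not replace HBV DNA, which is the stated trigger for stopping. Amendment 8 still carries the dosing schedule and applies to all centers, and the documents do not say when dosing ended.

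**Conclusion.** The concern holds. For the Treatment Period, Table 6-1 footnote f and Table 6-5 footnote b contradict Section 6.3.10.2. If the tables are followed, an admitted anti-HBc-positive completer has none of the 4 required on-treatment tests and receives all 15 dosing visits without an HBV DNA result on which to act. The Appendix 3 HBV DNA rule reaches no eligible subject.

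These figures are conditional: they describe a site that follows the footnotes, not one that follows Section 6.3.10.2. They assume that the 12-week interval runs from the first dose and that the laboratory manual does not override the tables. The number of anti-HBc-positive subjects is not given, so the total effect cannot be stated. The conflict must be resolved because it disables a safety stopping rule for the subjects it was written for.

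**What to change.** 1. In Table 6-1 footnote f and Table 6-5 footnote b, add an exception: HBV DNA PCR at Weeks 12, 24, 36 and 48 for subjects whom Table 6-6 admits with monitoring, with a cross-reference to Section 6.3.10.2.
2. In Section 6.3.10.2, state the same on-treatment interval for the Japanese HBsAb-only group.
3. In Appendix 3, replace the HBsAg-positive condition so that quantitative HBV DNA is required at a liver stopping event in the subjects whom Table 6-6 admits with monitoring.
4. In SAP Section 12.6.2, align the sentence on sampling times. Its listing of all hepatitis data needs no change.

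The cost is wording. No visit is added, the on-treatment tests are already required by Section 6.3.10.2, and the liver-event assay is already in the Appendix 13 panel. The change log for Amendment 6, which was never implemented, contains a footnote f sentence on 12-weekly testing that could serve as a starting text.

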6.1. Critical Baseline Assessments

Information collected during the Screening Period assessments described below represents key data that identifies and defines subject baseline status. This information is critical for the evaluation and comparison of subsequent measurements and determinations.

Cardiovascular medical history/risk factors will be assessed at Screening/Baseline.

** In Japan, refer to [Appendix 2](#) for additional screening assessments for TB, Pneumocystis pneumonia, and interstitial pneumonia.**

6.1.1. Medical History

A complete medical history will be taken at the Screening Visit. Information from the medical history is important to establish the baseline condition of the subject, and will impact the safety monitoring assessments during the study. Any significant medical conditions affecting the subject in the past 5 years should be recorded on the Medical Conditions page of the eCRF. The history should include the following:

- A thorough review of systems, including any past or current conditions
- Prior surgical procedures
- Pharmacotherapy and chronic or recent use of any medication
- Prior immunosuppressive therapies, including type, number, and duration
- Allergies and significant allergic reactions
- Significant infections, or history of recurrent infection, including urinary and respiratory tract infections
- Smoking history (current or previous smoker, number of packs a day smoked)

6.1.2. Pemphigus Vulgaris History

Details of the subject's PV history will be collected (eg, dates of symptom onset, diagnosis, and flares/relapses) in the eCRF. These data are critical for establishing subject eligibility, as well as establishing a baseline for subsequent clinical assessments.

The date of each subject's most recent failed steroid taper that resulted in a disease flare/relapse at a prednisone/prednisolone dose >10 mg/day will be collected in the eCRF. Additionally, a historical assessment of pemphigus clinical severity at the time of the failed steroid taper will be collected using the scale described in [Appendix 6](#).

6.2. Efficacy

[figure not shown]
[figure not shown]
6.2.1. Primary Efficacy Endpoints

[figure not shown]
Two co-primary efficacy endpoints will be evaluated:

- Time to sustained remission (SR) on minimal steroid therapy (defined as time from randomization to the time the subject initially tapered his/her oral prednisone/prednisolone dose to ≤ 10 mg/day and maintained ≤ 10 mg/day of oral prednisone/prednisolone with no new or nonhealing lesions for ≥ 8 weeks AND maintained that status until Week 60).
- Duration of remission on minimal steroid therapy (defined as total time [sum] of all periods of remission while on minimal steroid therapy [oral prednisone/prednisolone dose of ≤ 10 mg/day] up to Week 60).

6.2.2. Secondary Efficacy Endpoints

- Proportion of subjects achieving remission on minimal steroid therapy (defined as subjects who had an absence of new or nonhealing lesions while on an oral prednisone/prednisolone dose of ≤ 10 mg/day for ≥ 8 weeks) at Week 60.
- Time to remission while on minimal steroid therapy (defined as time from randomization to the time the subject initially tapered his/her oral prednisone/prednisolone dose to ≤ 10 mg/day and maintained ≤ 10 mg/day of oral prednisone/prednisolone with no new or nonhealing lesions for ≥ 8 weeks) by Week 60.
- Time to initial flare/relapse (defined as the time from randomization to the time that ≥ 3 new lesions within 1 month appear and do not heal spontaneously within 1 week, or to the time when there is an extension of lesions that were present at the randomization visit) by Week 60.
- Proportion of subjects who did not flare/relapse (defined as subjects who achieved remission on minimal steroid therapy and did not subsequently have a flare of disease) by Week 60. A flare/relapse is defined as new lesions that do not heal spontaneously within 1 week, or when there is an extension of lesions that were present at the randomization visit.
- Time to remission off steroid therapy by Week 60 (defined as the time from randomization to the time the subject initially tapered off all steroids for ≥ 8 weeks with an absence of new or nonhealing lesions).
- Proportion of subjects achieving remission while off steroid therapy by Week 60.
- Number of days a subject maintained minimal steroid therapy (an oral prednisone/prednisolone dose of ≤ 10 mg/day in the absence of new or nonhealing lesions) by Week 60.
- Cumulative dose of corticosteroids.

6.3. Safety

The following safety endpoints will be assessed:

[figure not shown]
- Adverse events
- Adverse event frequency, severity, and relationship to investigational product
- Frequency and severity of infections
- Frequency of SAEs
- Frequency of withdrawals due to treatment-related AEs.
- Frequency of AEs leading to permanent discontinuation of investigational product.
- Frequency of AEs of special interest, postinjection systemic reactions, and injection site reactions.
- Change from baseline in vital signs.

- Frequency of vital signs of clinical concern.
- Change from baseline in laboratory (hematology, chemistry, and urinalysis) parameters.
- Frequency of laboratory (hematology, chemistry, and urinalysis) results of potential clinical concern.
- Immunogenicity as measured by the incidence, titer, and type of HAHA immune response.

6.3.1. Liver Chemistry Stopping and Follow-up Criteria

[figure not shown]
Liver chemistry stopping and follow-up criteria have been designed to ensure subject safety and evaluate liver event etiology (in alignment with the Food and Drug Administration premarketing clinical liver safety guidance). Liver safety required actions and follow-up assessments can be found in [Appendix 3](#).

Figure 6-2 Liver Chemistry Stopping and Increased Monitoring Algorithm

Abbreviations: ALT=alanine aminotransferase; INR=international normalized ratio; SAE=serious adverse event; ULN=upper limit of normal.

Figure 6-3 Liver Chemistry Increased Monitoring Algorithm with Continued Therapy for ALT \geq 3xULN but $<$ 8xULN

Abbreviations: ALT=alanine aminotransferase; bili=bilirubin; INR=international normalized ratio; SAE=serious adverse event; ULN=upper limit of normal.

